**Table 5: Imputation Rules for Missing Data in the Primary Immunogenicity Analysis**

	Baseline a	Visit Week 12	Visit Week 26	Result/Imputation Rule
1.	x	x	x	No imputation.
2.	x	x	o	Subject will be counted as developing a treatment-induced AIA, impute visit Week 26 as positive result
3.	x	o	x	Subject will be counted as developing a treatment-induced AIA, impute visit Week 12 as positive result
4.	x	o	o	Subject will be counted as developing a treatment-induced AIA, impute visit Week 12 and visit Week 26 as positive result
5.	o	x	x	Subject will be counted as developing a treatment-induced AIA if visit Week 12, visit Week 26, or unscheduled assays up to visit Week 26 indicate positive result; otherwise, subject will be counted as not developing a treatment-induced AIA (all assays up to visit Week 26 are negative).
6.	o	x	o	Subject will be counted as developing a treatment-induced AIA, impute visit Week 26 as positive result
7.	o	o	x	Subject will be counted as developing a treatment-induced AIA, impute visit Week 12 as positive result
8.	o	o	o	Subject will be counted as developing a treatment-induced AIA, impute visit Week 12 and visit Week 26 as positive result

AIA = anti-insulin antibodies; o = AIA data missing, x = AIA data not missing.

a No imputation will be performed for missing baseline values.

Additional sensitivity analyses on the imputation, which explore the limitation(s) of the data or assumption(s) of the primary analysis being evaluated in each sensitivity analysis and how the analysis addresses each, will also be discussed in the SAP.

Missing data will be imputed for the HbA1c analysis. The robustness of the imputation will be explored via sensitivity analyses using multiple imputation and including a tipping point analysis. Full details of the multiple imputation procedure will be presented in the SAP.

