5.1 Sample Size and Power

Enrollment was planned for 550 subjects overall (275 subjects per treatment group). The primary analysis for the immunogenicity primary endpoint was to be an equivalence test for the difference in proportion of subjects who develop treatment-induced AIAAs between Gan & Lee insulin Glargine Injection and Lantus® using the 2 Wald one-sided tests (TOST) with $\alpha=0.05$ (Chow and Shao 2002 (1)). After scientific and regulatory review, the method to evaluate immunogenicity equivalence will be the 90% confidence intervals of risk difference from the logistic regression analysis (see Section 3.1). Under this newly adopted approach, no power loss is expected.

This sample size of 275 subjects per treatment group was chosen to achieve over 80% power using the TOST equivalence test for two proportions, a risk difference of zero and equivalence margins dependent on the observed treatment-induced AIA rate per Table 3 below. For example, a total sample size of 550 will provide approximately 85% power for the TOST equivalence test using a treatment-induced AIA rate of 30% and a margin of 12% (Table 3). The treatment-induced AIA is defined as newly confirmed positive AIA development or important (at least a 4-fold) increase in AIA titers, after baseline and up to visit Week 26 (see the definition of Primary Endpoint in Section 6.1 and Section 7.2). No drop outs are considered in the calculation. A larger than expected early discontinuation rate was observed as part of study monitoring activities and therefore protocol amendment 3 approved on 25-Apr-2019 included procedures to encourage subjects to return for assessments even if they had discontinued treatment early.

The appropriate similarity margin, based on the actual observed event rate for the intended reference product, will be used for final analysis after database lock as summarized in Table 3 below. The power calculation in the table was adapted for a sample size of 550 using the treatment-induced AIA rate for the reference product. Linear interpolation will be used for values between AIA rates in the table.

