11.6.1 Primary Endpoint

11.6.1.1 Incidence of Treatment-Induced Anti-Insulin Antibodies

Incidence of treatment-induced AIA is defined as subjects develop newly confirmed positive AIA or have important (4-fold) increase in AIA titer up to visit Week 26. The objective of the primary immunogenicity analysis will be to evaluate equivalence of Gan & Lee Insulin Glargine Injection to Lantus® by comparing the limits of the 90% confidence interval (CI) of country-adjusted difference in proportions of treatment-induced AIA development to the specified margins (-margin, +margin) where the margin is dependent on the unadjusted treatment-induced AIA rate in Lantus® and is defined in Section 5.1, Table 3.

The estimand of interest is the country-adjusted difference in treatment-induced AIA rates regardless if all subjects tolerate or adhere to study treatment or receive other insulin treatments. Intercurrent events will be handled according to the treatment policy strategy. Treatment Policy strategy is defined as the strategy that considers "The occurrence of the intercurrent event is irrelevant: the value for the variable of interest is used regardless of whether or not the intercurrent event occurs" (See ICH E9 R1 addendum). All AIA data collected, scheduled and unscheduled, will be considered for the analysis, even if collected after the occurrence of intercurrent events of (1) discontinuing study treatment, (2) returning to initial treatment and/or (3) initiating a new treatment.

Any treatment-induced AIA after baseline and up to visit Week 26 will have the subject count as treatment-induced AIA for the primary endpoint. The visit window (defined in Section 7.1) will only be limited to include assessment within 210 days from the first dose.

Missing data will be handled as described in Section 11.6.1.2. The SS will be used for the primary analysis.

The number and percentage of subjects in each treatment group who develop treatment-induced AIA as defined in Section 7.2 after baseline and up to visit Week 26 (upper limit of the visit window) will be evaluated using a logistic regression model adjusted by country (CNTRY) estimating the country-adjusted difference in proportions along with the corresponding 90% confidence interval (CI).

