Equivalence in difference in proportion δ between Gan & Lee Insulin Glargine Injection (π_1) and Lantus® (π_2) will be tested by comparing the limits of the 90% CI for treatment-induced AIA development with the following null hypothesis:

$$H_0: (\pi_1 - \pi_2) \leq -\delta_0 \text{ or } (\pi_1 - \pi_2) \geq \delta_0$$

Against the alternative hypothesis of:

$$H_1: -\delta_0 < (\pi_1 - \pi_2) < \delta_0$$

where δ_0 is the margin dependent on the observed unadjusted treatment-induced AIA rate in Lantus® (π_2) and is defined in Section 5.1, Table 3.

To evaluate equivalence of Gan & Lee Insulin Glargine Injection to Lantus® the calculated 90% CI has to be entirely contained with the interval $(-\delta_0, \delta_0)$.

A sample SAS code fragment is provided below for reference:

Category	Sample Availability	Imputation	Likely Scenarios
		
 Subject will be counted as 'NOT developing a treatment-induced AIA' if both Week 12 and Week 26 results are negative. 	
4	Any positive results from unscheduled (or out of window) AIA sample(s) during the Treatment Period	
 Positive result from unscheduled AIA sample will be treated the same way as the Week 12/26 samples when baseline result is present. Positive result from unscheduled AIA sample will render the subject as 'developing a treatment-induced AIA' if baseline sample is missing. 	
 Sample collection out of the allowable sample collection window. Sample collection due to other protocol deviations.

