11.6.1.3 Sensitivity Analyses

Inherent in the primary endpoint analysis described above are several implicit assumptions that can possibly affect the generalizability of immunogenicity. There are four assumptions that are important to mention. The primary analysis assumes that the impact on the immunogenicity conclusion of early discontinuations, important protocol deviations, less than full treatment duration and patterned missing data is negligible. Although the scientific rationale to make these assumptions is reasonable, sensitivity analyses for the primary endpoint of immunogenicity to assess the impact of these effects are planned, as follows:

- 1) Composite Strategy: Subjects in the SS with the intercurrent event of discontinuing treatment will be considered as having a treatment-induced AIA. Results of assessment after the end of treatment are excluded from the analysis. The imputation approach as described in Table 4 will be used for missing data. This sensitivity analysis will examine the assumption that results were not impacted by the discontinuation of treatment (as these will be imputed as positive immune response).
- 2) Per Protocol Analysis Set (PPS): Subjects with any important protocol deviations (as defined in Section 11.3) will be excluded from the analysis. For subjects in the PPS, the imputation approach as described in Table 4 for primary analysis will be followed. In the primary analysis, subjects with important protocol deviations could falsely draw the estimated treatment difference closer. Exclusion of these subjects in this sensitivity analysis will help assess the magnitude, if any, of this effect.
- 3) SS – Completers: This analysis will not use any imputation of missing data. Only subjects with valid baseline and visit Week 12 and Week 26 assessments conducted within the required visit window (visit Week 12 \pm 1 week and visit Week 26 \pm 4 weeks, respectively) and who had treatment until visit Week 26 will be used for the analysis. Subjects with less than a full treatment duration could underestimate the proportion of subjects reporting positive immune response. By including only completers, as in this sensitivity analysis, this estimated treatment difference is determined only by subjects whose treatment duration was full.

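### The primary equivalence margin is read from the trial's own Lantus rate and then treated as known, so the one-sided error for a more immunogenic test product is about 6.0–7.1% at Lantus rates of 10–28% and 5.8% at 30%, not 5%

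*SAP*

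**What the plan says.** SAP 11.6.1.1 writes the null hypothesis with δ₀ as a "margin dependent on the observed unadjusted treatment-induced AIA rate in Lantus". The text above the hypotheses says the same: "the margin is dependent on the unadjusted treatment-induced AIA rate in Lantus". To conclude equivalence, "the calculated 90% CI has to be entirely contained with the interval" from −δ₀ to +δ₀. SAP 5.1 adds "Linear interpolation will be used for values between AIA rates in the table", and Protocol 12.2 and 12.7.1 describe the same margin. The level is α = 0.05 for each one-sided test.

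The sample size of 275 per arm "was chosen to achieve over 80% power using the TOST equivalence test for two proportions, a risk difference of zero". Protocol Table 4 lists a margin and a power for each reference rate from 10% to 90%, but no type I error.

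Two further points affect the observed Lantus rate. Protocol Table 5 counts missing post-baseline results as events, for example "Subject will be counted as developing a treatment-induced AIA, impute visit Week 26 as positive result". SAP 5.1 reports that "A larger than expected early discontinuation rate was observed as part of study monitoring activities".

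In SAP 11.6.1.3, "sensitivity analyses for the primary endpoint of immunogenicity to assess the impact of these effects are planned, as follows". The four assumptions named there are early discontinuation, important deviations, short treatment duration and patterned missing data. That the margin is known is not among them.

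**The concern.** A 90% CI inside fixed limits gives a 5% one-sided test. Here the limits are an estimate from the same data. The upper-side comparison is whether RD − m(p̂₂) is below zero, where RD = p̂₁ − p̂₂ and m is the interpolated margin. Below a Lantus rate of 50% the table margin rises with the rate. A Lantus rate that is high by chance therefore lowers RD and raises m, and both movements favour equivalence. The CI accounts only for the first.

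The side affected is the one a biosimilar trial has to control: declaring equivalence when the test product is more immunogenic by the whole margin. The same mechanism makes the rule too strict against a less immunogenic product.

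**Working it through.** **Inputs.** 275 per arm, 1:1, no dropout, one-sided α = 0.05 (Protocol 12.2, SAP 5.1). Margins from Protocol Table 4: 7.9, 9.3, 10.5, 11.3, 12.0, 12.5, 12.8, 13.0 and 13.1 points at 10, 15, 20, 25, 30, 35, 40, 45 and 50%, symmetric above 50%, with linear interpolation. CI: unadjusted Wald without continuity correction (Protocol synopsis); the SAP's country-adjusted interval is checked below. Two assumptions: the null boundary is the table margin at the true Lantus rate, and the margin is flat below 10%, where the table gives none.

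**The plan's own figure.** Power = 2Φ(m/SE − 1.645) − 1. At 30%, SE = √(2 × 0.30 × 0.70/275) = 0.0391, so power = 2Φ(0.12/0.0391 − 1.645) − 1 = 84.6% (84.9% by exact enumeration). The stated figure of about 85% is reproduced.

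**How much the margin moves.** At a true rate of 15% the observed Lantus rate has a 90% range of 11.6–18.5%, so the margin used ranges from 8.4 to 10.2 points.

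**Variance.** Let V₁ and V₂ be the binomial variances of the two observed rates and m′ the slope of the margin table: 0.28 between 10 and 15%, 0.24 between 15 and 20%, 0.16 falling to 0.10 over 20–35%, and 0.06 or less from 35 to 50%.

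- Variance used by the CI: V₁ + V₂
- Actual variance, upper side: V₁ + (1 + m′)²V₂
- Actual variance, lower side: V₁ + (1 − m′)²V₂

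At 15%, the boundary test rate is 24.3% and the mean adjacent slope is 0.26. V₁ = 0.243 × 0.757/275 = 0.000669 and V₂ = 0.15 × 0.85/275 = 0.000464. The SE used is 3.37 points and the actual SE is 3.75 points, so the error is Φ(−1.645 × 3.37/3.75) ≈ 7.0%. At 30% (slope 0.12) the SEs are 4.06 and 4.29 points and the error is about 6.0%.

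**Exact error.** Binomial(275, p₁) × Binomial(275, p₂) probabilities were summed over the outcomes that declare equivalence, at p₁ = p₂ + m(p₂) for the upper side and p₁ = p₂ − m(p₂) for the lower side.

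| True Lantus rate | Upper side, plan's rule | Upper side, fixed margin | Lower side, plan's rule |
|---|---|---|---|
| 10% | 7.1% | 5.1% | 6.1% |
| 12.5% | 7.1% | 5.1% | 3.0% |
| 15% | 6.9% | 5.1% | 2.4% |
| 20% | 6.3% | 5.1% | 2.8% |
| 25% | 6.1% | 5.0% | 3.5% |
| 28% | 6.0% | 5.0% | 3.7% |
| 30% | 5.8% | 4.9% | 3.8% |
| 35% | 5.4% | 5.0% | 4.0% |
| 40% | 5.4% | 4.9% | 4.4% |
| 44% | 5.0% | 5.0% | 4.5% |

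Holding the margin fixed at the same boundary restores about 5% on the upper side, which isolates the cause. The 6.1% on the lower side at 10% also appears with a fixed margin, so it is a Wald effect and a separate matter. Above about 55% the pattern mirrors. A Monte Carlo check with 4 million trials agrees (7.09% at 10%, 6.24% at 20%, 5.78% at 30%).

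**The SAP's country-adjusted interval.** A simulated logistic risk difference (200,000 trials per setting, four hypothetical countries, three degrees of heterogeneity) gives 7.1–7.2% at 10%, 6.3–6.4% at 20%, 5.9–6.0% at 28% and 5.7–5.8% at 30%. With a fixed margin it gives 4.9–5.3%.

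**Missing counted as positive.** If a fraction q is missing in both arms, a true rate p becomes p(1 − q) + q. With q assumed at 5, 10 and 15%, a true 15% becomes 19.3, 23.5 and 27.8%, with errors of 6.4, 6.2 and 6.0%. A true 30% becomes 33.5, 37 and 40.5%, with errors of 5.4, 5.5 and 5.3%. The excess shrinks but remains.

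**The case against.** The strongest objection is to the benchmark. The documents openly choose a margin at the observed rate, and nowhere say that the boundary is the table margin at the true rate. That is correct. But a null hypothesis containing a sample statistic fixes no population boundary, and a stated α needs one. The true-rate margin is the natural choice. The finding is conditional on it.

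The excess is also modest where the documents point. The only worked example is 30%, where it is 0.8 points. Nothing supplied predicts a rate of 10–28%, and imputing missing results as positive pushes the rate upward. Put as a margin, the plan's rule reaches exactly 5% error at a true difference of about 12.3 points instead of 12.0 at a Lantus rate of 30%, 10.9 instead of 10.5 at 20%, and 9.9 instead of 9.3 at 15%. This limits the weight of the point but does not remove it.

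Parts of the SAP are not in the public text: its Table 3, section 11.6.1.2, the code fragment and the end of 11.6.1.3. Protocol Table 4 stands in for Table 3, and an analysis of this kind could in principle sit in the missing part.

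Finally, a rule that carries the margin's error is not stricter everywhere. It relaxes the lower side, where its own error reaches about 5.4% near a Lantus rate of 43%. At 42–44% its worse side slightly exceeds that of the plan's rule. This stands, and is a reason to use it as a sensitivity analysis and not as a replacement.

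**Conclusion.** The concern holds. Against the table margin at the true Lantus rate, the primary rule does not deliver its stated 5% on the side of a more immunogenic test product. The excess is 1 to 2.1 points at Lantus rates of 10–28%, 0.8 points at 30%, about 0.4 points at 35–40%, and nil by about 44%. The conclusion rests on the true-rate boundary, on Protocol Table 4 standing in for SAP Table 3, and on about 275 per arm. With 240 to 289 per arm the upper-side error is 5.85–7.11% at the rates checked from 10% to 28%, and 5.7–5.8% at 30%. The SAP's change to a country-adjusted interval does not remove the effect. This should be corrected in the SAP; it does not invalidate the design.

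**What to change.** Keep the prespecified primary rule and make two additions.

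1. In SAP 5.1 and 11.6.1.1, state that, against the table margin at the true Lantus rate, the one-sided error for a more immunogenic test product is about 5.8% at 30% and up to about 7% at 10–15%, and that the lower side is conservative over about 12.5–45%.
2. In SAP 11.6.1.3, add a sensitivity analysis that requires both
   - RD + 1.645·√(Var(RD) + m′²·Var(p̂₂) − 2m′·Cov(RD, p̂₂)) < m(p̂₂)
   - RD − 1.645·√(Var(RD) + m′²·Var(p̂₂) + 2m′·Cov(RD, p̂₂)) > −m(p̂₂)

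Use the table segment slope for m′, and 0 outside 10–90%. Name a convention at the table rows; the choice changes the error by less than 0.05 points. Take the variances and covariance jointly for the country-adjusted RD and the unadjusted Lantus rate, by delta method or bootstrap. State that the primary rule governs: a sensitivity failure is reported as a limitation, and a sensitivity pass does not rescue a failed primary analysis.

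Under this rule the upper-side error is 4.8–5.1% over Lantus rates of 10–40%. For example, with 41/275 Lantus positives (14.9%, margin 9.27 points) the plan's rule accepts 29–52 test positives and the sensitivity rule 27–50. With 82/275 (29.8%) the ranges are 67–96 and 65–95.

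The cost is two sentences and one analysis of existing data, with no loss of power for the primary test. At zero true difference the two rules would disagree in about 6% of trials at 15% (4.0% pass only the plan's rule, 2.1% only the sensitivity rule) and 2.8% at 30%. If the sponsor chose to make it primary, power would go from 83.9% to about 82.0% at 15%, 84.1% to 82.4% at 20% and 84.4% to 83.8% at 30%. The largest loss is about 2.2 points, near 17%, and power stays at or above 81.9% over 10–50%, still over the planned 80%.

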11.6.1.3 Sensitivity Analyses

Inherent in the primary endpoint analysis described above are several implicit assumptions that can possibly affect the generalizability of immunogenicity. There are four assumptions that are important to mention. The primary analysis assumes that the impact on the immunogenicity conclusion of early discontinuations, important protocol deviations, less than full treatment duration and patterned missing data is negligible. Although the scientific rationale to make these assumptions is reasonable, sensitivity analyses for the primary endpoint of immunogenicity to assess the impact of these effects are planned, as follows:

- 1) Composite Strategy: Subjects in the SS with the intercurrent event of discontinuing treatment will be considered as having a treatment-induced AIA. Results of assessment after the end of treatment are excluded from the analysis. The imputation approach as described in Table 4 will be used for missing data. This sensitivity analysis will examine the assumption that results were not impacted by the discontinuation of treatment (as these will be imputed as positive immune response).
- 2) Per Protocol Analysis Set (PPS): Subjects with any important protocol deviations (as defined in Section 11.3) will be excluded from the analysis. For subjects in the PPS, the imputation approach as described in Table 4 for primary analysis will be followed. In the primary analysis, subjects with important protocol deviations could falsely draw the estimated treatment difference closer. Exclusion of these subjects in this sensitivity analysis will help assess the magnitude, if any, of this effect.
- 3) SS – Completers: This analysis will not use any imputation of missing data. Only subjects with valid baseline and visit Week 12 and Week 26 assessments conducted within the required visit window (visit Week 12 \pm 1 week and visit Week 26 \pm 4 weeks, respectively) and who had treatment until visit Week 26 will be used for the analysis. Subjects with less than a full treatment duration could underestimate the proportion of subjects reporting positive immune response. By including only completers, as in this sensitivity analysis, this estimated treatment difference is determined only by subjects whose treatment duration was full.

11.6.2.3 Change in Anti-Insulin Antibody Titer

The change from baseline in AIA titers at visit Week 12 and visit Week 26 will be summarized descriptively in subjects with confirmed positive AIA at baseline. Though not specified in the protocol, this analysis is planned for the subset of subjects with confirmed positive AIA only.

11.6.2.4 Subjects with Confirmed Positive Anti-Insulin Antibodies Who Develop Newly Confirmed Neutralizing AIA

The percentage of subjects in each treatment group with newly confirmed neutralizing AIA after baseline and up to visit Week 26 will be compared using difference in proportions. The difference in proportions will be estimated along with the corresponding 90% CI in the SS using a country-adjusted logistic regression model.

Missing data will not be imputed, the percentages will be based on the subjects with documented confirmed positive AIA after baseline and up to visit Week 26.

11.6.2.5 Subjects with Confirmed Positive Anti-Insulin Antibodies

The percentage of subjects in each treatment group with confirmed positive AIA after baseline and up to visit Week 26 will be compared using difference in proportions. The difference in proportions will be estimated along with the corresponding 90% CI in the full SS using a country-adjusted logistic regression model.

Missing data will be imputed as described for the primary endpoint in Table 4.

11.7 Efficacy Analyses

11.7.1 Key Secondary Endpoint

An overview of planned analyses for the key secondary endpoint of change from baseline in HbA1c, including sensitivity analyses, is provided in Table 5 below.

Table 5: Overview of key secondary endpoint analyses

Analysis	Population used	Analysis Details	Section reference
1. Main analysis	Full analysis set	Treatment Policy Estimand - ANCOVA using MI under the assumption of MNAR; this analysis uses unscheduled HbA1c results from discontinued subjects to impute missing in each treatment arm.	Section 11.7.1.1 Change from Baseline in HbA1c at 26 weeks
2. Sensitivity analysis	Per protocol analysis set	ANCOVA using MI under the assumption of MNAR; this analysis uses the same approach for imputation as the main analysis. Used to assess the robustness of main analysis to important deviations from the protocol.	Section 11.7.1.3 Sensitivity Analyses - PPS
3. Sensitivity analysis	Full analysis set of completers	ANCOVA without imputation. This analysis is used to assess the robustness of main analysis to subjects lost to follow-up.	Section 11.7.1.3 Sensitivity Analyses - FAS completers

For subjects who discontinue from treatment before visit Week 26 or who have no HbA1c measurement at visit Week 26, HbA1c will be assigned to the scheduled time point if they fall within the upper limit of visit window defined in Section 7.1 (that is, for study day ≤ 210).

Submissions to Food and Drug Administration (FDA) and European Medicines Agency (EMA) require different methods for efficacy HbA1c evaluation.

For FDA submission, equivalence in change from baseline in HbA1c between Gan & Lee Insulin Glargine Injection (μ_1) and Lantus® (μ_2) will be tested using the two one-sided tests (TOST) approach proposed in Schuirmann (1987) (7) with the following null hypothesis:

$$H_0: (\mu_1 - \mu_2) \leq -0.4 \text{ or } (\mu_1 - \mu_2) \geq 0.4$$

Against the alternative hypothesis of:

$$H_1: -0.4 < (\mu_1 - \mu_2) < 0.4$$

with $\alpha=0.05$.

The 90% CI will be estimated using a pattern mixture model that uses multiple imputation (MI) analyzed using Analysis of Covariance (ANCOVA) with treatment and stratification factor of country (CNTRY) included as fixed effects and baseline HbA1c included as a covariate. Separately in each treatment group, the imputation will use outcomes in subjects who discontinued treatment prior to Week 26 but returned to provide a visit Week 26 HbA1c sample to impute outcomes in subjects without actual visit Week 26 recorded results under the MNAR assumption. Limits of the imputed value will use the minimum of HbA1c values and the maximum of all HbA1c values assessed, and rounded to the nearest integer. These values are found in the database to be minimum as 5 and the maximum as 13. No imputation will be performed for missing baseline HbA1c. Equivalence will be assessed based on the 90% CI; no p-values will be computed. Change from baseline in HbA1c between Gan & Lee Insulin Glargine Injection and Lantus® will be considered equivalent if the 90% CI is within the margins (-0.4%, 0.4%).

For EMA submission, non-inferiority in change from baseline in HbA1c between Gan & Lee Insulin Glargine Injection and Lantus® will be tested using the following null hypothesis:

$$H_0: (\mu_1 - \mu_2) \geq 0.4$$

Against the alternative hypothesis of:

$$H_1: (\mu_1 - \mu_2) < 0.4$$

with a 1-sided $\alpha=0.025$.

In addition, the same non-inferiority test with a margin of 0.3% will be performed.

The 95% CI will be estimated using a pattern mixture model that uses MI analyzed using ANCOVA with treatment and stratification factor of country (CNTRY) included as fixed effects and baseline HbA1c included as a covariate. Separately in each treatment group, the imputation will use outcomes in subjects who discontinued treatment prior to Week 26 but returned to provide a visit Week 26 HbA1c sample (labeled as the unscheduled) to impute outcomes in subjects without actual visit Week 26 recorded results under the MNAR assumption. No imputation will be performed for missing baseline HbA1c.

Analysis of HbA1c will follow a hierarchical testing strategy: first, non-inferiority will be tested using a margin of 0.4% and only if this test is significant, then non-inferiority will be tested using a margin of 0.3%.

Non-inferiority will be assessed based on the 95% CI; no p-values will be computed. Change from baseline in HbA1c between Gan & Lee Insulin Glargine Injection and Lantus® will be considered non-inferior if the 95% CI is below the margins of 0.4 and 0.3%, respectively.

